#### **Sample Size Calculations and Study Power**

The power calculation is primarily based on the study aims for comparative effectiveness. The original power calculation was for  $N = 850$ , with  $N = 750$  patients completing the month-12 survey. The study sample size was later reduced to  $N = 489$  participants completing the month-12 survey ( $n = 163$  patients per intervention arm on average). As a result, the study's power is lower than initially planned but remains adequate for the objectives, summarized as follows:

*Hypothesis 1a.*  $N = 163$  Taper Only participants provide 80% power to confirm that the taper success rate is above 40% at a two-sided significance level of 0.05, when the true success rate is 51.5%.

*Hypothesis 1b.* Comparing the taper success rate between  $n = 140$  Taper Only participants with an initial dose  $< 200$  MEDD and  $n = 23$  Taper Only participants with an initial dose  $\geq 200$  MEDD, the expected 95% confidence interval (CI) for the difference in success rates is [-22%, 22%], assuming a true taper success rate of 50% independent of the initial dose. The width of the CI increases by only 24% due to the sample size reduction.

*Hypothesis 2a.*  $N = 163$  participants per intervention arm provide 80% power for detecting a taper success rate difference of 40% versus 53.5% at a two-sided significance level of 0.05.

*Hypothesis 2b.*  $N = 163$  participants per intervention arm yield an expected 95% CI of [-11%, 11%] for estimating the difference in taper success rates between the Taper + pain-CBT and Taper + CPSMP arms, assuming a taper success rate of 50% in both arms.

*Hypothesis 2c and 2d.*  $N = 163$  participants per intervention arm provide 80% power to detect a between-group difference of 0.311 standard deviation in the 12-month change of continuous outcomes using a two-sample t-test at a two-sided significance level of 0.05.

We also assume an annual drop off rate is less than 19% and we will include all drop outs in our ITT analyses. We will enroll a total of 594 patients to assure the minimum group size requirements for analysis of comparative effectiveness.

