We will compare the intervention success rate between participants who received the behavioral interventions with participants who received Taper Only using Fisher's exact test. The difference in success rates between Taper + pain-CBT and Taper + CPSMP will be assessed with 95% confidence intervals (CI) to determine equivalence. Secondary outcomes—including pain intensity, pain interference, depression, self-efficacy, and satisfaction with roles and activities—will be compared between Taper + pain-CBT and Taper Only and between Taper + pain-CBT and Taper + CPSMP at months 6 and 12 using mixed effects model for repeated measurements regression. This analysis will incorporate baseline, month 6, and month 12 outcomes as dependent variables, with an unstructured variance-covariance matrix for within-subject correlations.

***Exploratory Hypothesis 2e:*** We will separately estimate the probability of opioid escalation by intervention arm (pain-CBT, CPSMP and Taper Only).

For exploratory hypotheses, the probabilities of opioid escalation by intervention group will be estimated and compared with Fisher's exact test. Post-hoc analyses will use logistic regression to examine associations between baseline characteristics and tapering success. There is no correction for multiple comparisons. Heterogeneity of treatment effects will be explored by splitting the population into training and validation sets of equal sizes. Logistic regression with lasso regularization will identify baseline features predicting tapering success in each intervention group. These models will be applied to testing sets to identify the subgroup with the highest predicted success under Taper + pain-CBT, and success rates will be compared across intervention arms within the subgroup. Intervention effects will be also estimated in predefined subgroups.

Heterogeneity of treatment effects will be explored for each intervention arm considering gender, age, race, initial opioid dose, baseline depression, and anxiety level.

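### The heterogeneity analysis estimates effects in subgroups but includes no estimate or test of whether the effect differs between them

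*Combined protocol and SAP*

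**What the plan says.** The Statistical Analysis Plan describes heterogeneity in the paragraphs that follow exploratory Hypothesis 2e. There are three elements.

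- A split-sample step: "Logistic regression with lasso regularization will identify baseline features predicting tapering success in each intervention group". The subgroup with the highest predicted success under pain-CBT is then picked out in the held-out half, and "success rates will be compared across intervention arms within the subgroup".
- Subgroup estimation: "Intervention effects will be also estimated in predefined subgroups".
- A list of factors: "Heterogeneity of treatment effects will be explored for each intervention arm considering gender, age, race, initial opioid dose, baseline depression, and anxiety level".

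The same section states: "There is no correction for multiple comparisons". No interaction term, interaction test or interval for a difference between subgroup effects appears anywhere in the document, and no rule is given for reading the subgroup estimates. Elsewhere the section does name its methods: exact, chi-square and Fisher tests, t-tests, analysis of covariance and a repeated-measures mixed model.

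**The concern.** Heterogeneity of effect is a difference between effects. None of the three elements estimates that difference. Subgroup estimates give two effects and leave the reader to compare them informally. The lasso step ranks patients by predicted success under one arm, which is prognosis, and compares arms inside the chosen subgroup without a contrast against the remaining patients. If the list of factors means analyses within each arm, those associations are prognostic too until they are compared across arms.

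What is at stake is interpretation. With no contrast specified, the easiest comparison is between subgroup p-values, and in a trial sized for its overall effect that comparison often disagrees by chance. The Project Summary says the study is meant to help patients and prescribers choose between strategies, and the CPSMP description under Study Arms suggests that some people may respond better to one program than the other. Differences between subgroups are therefore likely to attract attention.

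**Working it through.** **Inputs.** From Sample Size Calculations and Study Power: 163 month-12 completers per arm ("patients per intervention arm on average"), and a statement that this number will "provide 80% power for detecting a taper success rate difference of 40% versus 53.5"%, two-sided 0.05. Hypothesis 2a pools the two behavioral arms against Taper Only, so the comparison is 326 v 163. (The Hypothesis 2a analysis text still carries 500 v 250 from the larger design; the reduced numbers are used here.) Assumptions that are not in the documents: two-level factors, splits of 50:50 and 80:20, the same split in every arm, and the reading rule of significant in one subgroup but not in the other.

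**Step 1: reproduce the stated power.** Power = Φ[(Δ − 1.96·s₀)/s₁], where s₀ = √[p̄(1−p̄)(1/n₀+1/n₁)] and s₁ = √[p₀(1−p₀)/n₀ + p₁(1−p₁)/n₁].
- p̄ = (163×0.40 + 326×0.535)/489 = 0.490; s₀ = 0.0480; s₁ = 0.0473.
- (0.135 − 1.96×0.0480)/0.0473 = 0.87, so power is 0.807. The stated 80% is reproduced by the pooled comparison. One behavioral arm against Taper Only (163 v 163) gives 0.687.

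**Step 2: same true rates in both subgroups.** P(exactly one significant) = a(1−b) + b(1−a), where a and b are the powers in the two subgroups.

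| Split | Power in each subgroup | Exactly one significant |
|---|---|---|
| 50:50 | 0.512 and 0.512 | 2×0.512×0.488 = 0.50 |
| 80:20 | 0.714 and 0.239 | 0.714×0.761 + 0.239×0.286 = 0.61 |

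Simulation of 20,000 trials gave 0.499 (chi-square) and 0.498 (Fisher) for 50:50, and 0.620 and 0.618 for 80:20.

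**Step 3: vary the common effect (50:50, 326 v 163).**
- 40% v 45%: power 0.111 in each half, so 2×0.111×0.889 = 0.20.
- 40% v 50%: 0.43.
- 40% v 60%: 0.26.
- No effect: 2×0.05×0.95 = 0.095 (simulation 0.097 chi-square, 0.077 Fisher).

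For equal halves the maximum of 2a(1−a) is 0.50, reached at a = 0.5. The design effect happens to sit almost exactly there.

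**Step 4: interaction test.** In the same simulations a log-odds-ratio interaction test at two-sided 0.05 rejected in 5.0% (50:50) and 4.5% (80:20) of trials with identical effects.

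**Step 5: six factors, no effect anywhere.** Each patient belongs to one subgroup of every factor, so all subgroup statistics share the overall result. For a 50:50 factor, subgroup z = (overall z ± interaction z)/√2. Simulating 1,000,000 trials with six independent factors gives about a 32% chance of at least one significant subgroup (also about 32% with 80:20 splits). Six independent unadjusted interaction tests give 1 − 0.95⁶ = 26%.

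**Step 6: power of the interaction test.** With a 50:50 split the standard error of the difference between subgroup effects is twice that of the overall effect. At 80% overall power the overall noncentrality is 1.96 + 0.84 = 2.80. An interaction as large as the main effect therefore has noncentrality 1.40 and power Φ(1.40 − 1.96) = 0.29. For two single arms (163 v 163) and the same 13.5 points, s₁ = 0.0548, so noncentrality is 0.135/0.0548/2 = 1.23 and power is Φ(1.23 − 1.96) = 0.23.

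**The case against.** The strongest reply has four parts.

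- *The plan promises estimates, not a comparison of p-values.* This is correct. The 50% and 61% figures depend on a reading rule that the plan does not contain, and on a true effect near 40% v 53.5%. They are conditional figures. What stands without them is that no estimate of the difference is planned.
- *The sentence on exploring heterogeneity for each arm is ambiguous.* It may simply list the factors for the predefined subgroups. A reader might infer that the plan commits itself to within-arm prognostic analyses and calls them treatment effects; the text does not settle that. On either reading, a contrast between subgroup effects is missing.
- *The work is exploratory.* The plan says so, and it openly states that there is no multiplicity correction. No numbered hypothesis or power statement rests on this analysis. That lowers the stakes, but exploratory status does not make a set of separate estimates answer a question about their difference. The documents do not support the further inference that care will be directed by gender, race or dose on the strength of these results.
- *Interaction tests are weak.* They are, as Step 6 shows. A wide interval for the interaction shows that weakness openly, whereas separate subgroup p-values conceal it.

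The held-out half in the lasso step guards against overfitting but supplies no contrast with the other patients.

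**Conclusion.** The point holds as a gap in an exploratory analysis: the plan names heterogeneity of effect as its target and specifies nothing that estimates it. The primary analysis is unaffected.

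The size is conditional. Per two-level factor, with the Hypothesis 2a rates identical in both subgroups and the significant-here, not-there reading, the false impression of differential benefit arises in about 50% of trials (50:50) or 61% (80:20), against about 5% with an interaction test. The 50:50 figure drops to about 20% for a 5-point effect and to 10% or less with no effect.

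Two stronger readings fail. A reader might infer that the plan will mislead half the time whatever the truth; Step 3 shows that this is close to the worst case for equal halves. A reader might also multiply 0.95 twelve times and infer a 46% chance of some significant subgroup under no effect. That treats the twelve tests as independent when they share patients. The figure is about 32%, and the like-for-like figure for six unadjusted interaction tests is about 26%. On that measure the gain is modest; the main gain is that the analysis addresses the question asked.

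**What to change.** For each of the six factors, add arm-by-factor interaction terms to the logistic model already planned for taper success and to the mixed model already planned for the continuous outcomes, evaluated at month 12. Do this for behavioral v Taper Only and also for pain-CBT v CPSMP, because pooling the behavioral arms cannot show whether some patients do better on one program than on the other. Keep starting MEDD, age and depression continuous. Report each interaction estimate with its 95% CI, show the subgroup estimates beside it, and label the results exploratory and unadjusted for multiplicity. Reword the sentence about exploring heterogeneity for each arm so that it says which contrast is meant.

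The cost is SAP wording and a few model terms, with no new data, patients or visits. The drawback is low power: about 29% for an interaction as large as the main effect with a 50:50 split, and lower for pain-CBT v CPSMP. A non-significant interaction must not be read as evidence of a uniform effect.

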EMPOWER Patient-Centered Opioid Taper (received by all three study arms). Following study enrollment, all participants will engage with their EMPOWER clinician in a patient-centered prescription opioid tapering program. All opioid prescribing will be managed by the EMPOWER clinician. Opioid dose data will be sourced from study surveys and the patient's electronic medical record. All aspects of tapering will be individualized, including the timing of taper initiation, the dose reduction goal (set collaboratively with the patient), and the pace of the taper. The basic patient-centered opioid taper protocol will mirror the pilot methods described in Darnall et al. Importantly, complete opioid cessation will only be a goal if the patient chooses it. The recommended taper speed will be a 5% reduction of the starting dose, with one dose decrease per month until the patient is stable, without physical discomfort or psychological distress. Patients will be assessed at each visit; dose decreases or increases in taper speed will only occur after consultation with and consent from the patient. Patients will have the choice to set the pace of their taper, pause their taper, or withdraw from the taper or the study at any time. The taper will not be unidirectional: EMPOWER will not restrict needed opioid increases for acute pain or for patients with poor responses to the taper. Participation in the study will not prevent patients from receiving any needed medical care. Patients will not be removed from the study if they increase their opioid dose; on the contrary, we will seek to follow these patients to understand their experiences, responses, and unmet treatment needs.

Clinicians may use the electronic CHOIR opioid taper tool to create a taper schedule that remains flexible based on patient responses to prior dose reductions. Micro-dose reductions will be recommended for the first few decrements, followed by dose reductions as tolerated, not exceeding a 10% opioid dose reduction per month. Recommendations will include tapering one opioid at a time and avoiding

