**(2) EMPOWER Taper + The Chronic Pain Self-Management Program (CPSMP).** CPSMP is an evidence-based behavioral treatment delivered by two certified healthcare clinicians or peer co-leaders with lived experience in successful pain self-management. Certification as a CPSMP leader requires 24 hours of training over four days. The CPSMP manualized protocol includes patient education about pain and strategies for effective self-management of pain, its impacts, and other symptoms. Based on self-efficacy theory, CPSMP is delivered in six weekly 2.5-hour group sessions to cohorts of 8–18 participants. All participants receive a book on pain self-management and an exercise CD. Like pain-CBT, CPSMP incorporates interactive discussions, relaxation training, action planning, and home exercises into each session. Patients learn to live better with chronic pain by making daily choices that support improved health and function. Participants assigned to this arm will not receive group pain-CBT during the study period. No other aspects of pain care will be constrained, including individual psychological treatment; receipt of non-study treatments will be tracked.

Prior research has shown that pain-CBT and CPSMP have both shared and distinct effects, suggesting some individuals may respond better to one treatment than the other. However, no evidence currently exists to guide a best-practice choice between the two. While pain-CBT and CPSMP are both effective for chronic pain, they have not been tested within an active opioid reduction protocol. We hypothesize that these behavioral interventions will help patients reduce opioids and associated risks, manage pain, and restore function in ways superior to opioid reduction alone.

**(3) EMPOWER Taper Only (usual care).** Participants assigned to this intervention arm will participate in the voluntary EMPOWER patient-centered opioid tapering program and will not receive group pain-CBT or CPSMP during the 12-month study period. No other aspects of pain care will be constrained.

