***Access and Intervention Participation.*** The comparison across interventions will be performed according to the intention-to-treat principle. Additional comparisons based on the actual intervention received will be conducted as a sensitivity analysis. We will also study the effect of intervention participation and on treatment outcomes. To this end, we will perform regression analyses to examine the association between the success rate for opioid weaning and other outcomes with session attendance for the pain-CBT and CPSMP arms, separately, while adjusting for identified confounding factors affecting compliance. We will also investigate how baseline factors, such as socioeconomic status, affect the level of compliance.

***Virtual Behavioral Treatment Groups: Comparison of participants who receive in person vs. virtual treatment -*** We will examine mode of delivery as a potential covariate in our analytic models, and study statistician [name] will both advise and implement. Outside of this issue of treatment delivery mode, we must also recognize that COVID itself has introduced a new variable in the study. We will be examining COVID impacts, as well. In regards to the group size and effectiveness of the intervention, the size of the virtual groups are comparable to the size of the in person groups where most groups have an average size of 4 participants. Facilitators stated larger groups (more than 4 participants per cohort) usually provide a more dynamic experience with diverse interactions. While in smaller groups, participants have a chance to go into more detail regarding the skills they are learning and using and any barriers that arise.

***Sensitivity Analysis.*** We will perform sensitivity analyses to account for missing data and non-completion of behavioral interventions. In addition, we will consider an alternative definition of taper success, replacing the 50% reduction in opioid dose with a 30% reduction in opioid dose. A 30% change has been cited as a benchmark for a moderately clinically important difference in the chronic pain literature. Similar analyses will be conducted with this new endpoint as part of the sensitivity analyses.

Statistical analysis will be completed using SAS Enterprise Guide Version 8.3 and R Version 4.1.1.

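### The as-received sensitivity analysis breaks randomization and, if attendance is related to prognosis, can show a behavioral effect in either direction when there is none; a complier average causal effect should replace it

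*Combined protocol and SAP*

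**What the plan says.** Under Access and Intervention Participation, the Statistical Analysis Plan sets the main rule: "The comparison across interventions will be performed according to the intention-to-treat principle". It then adds: "Additional comparisons based on the actual intervention received will be conducted as a sensitivity analysis". No attendance threshold, placement rule for non-attenders or covariate adjustment is given for this second comparison.

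Two related analyses appear nearby. One is a set of regressions of outcome on "session attendance for the pain-CBT and CPSMP arms, separately, while adjusting for identified confounding factors affecting compliance". The other, under Sensitivity Analysis, is a promise without a method: "We will perform sensitivity analyses to account for missing data and non-completion of behavioral interventions".

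Three design facts bear on the point:

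- The taper is common to all arms: "EMPOWER Patient-Centered Opioid Taper (received by all three study arms").
- Taper Only patients "will not receive group pain-CBT or CPSMP during the 12-month study period" (Study Arms).
- Appendix A has group attendance reported by participants and also recorded by staff.

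The paragraph after Hypothesis 2d also describes the main success-rate comparison in terms of participants who received the behavioral interventions, where one would expect participants assigned to them.

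**The concern.** The taper is the shared component, so a patient randomized to pain-CBT or CPSMP who attends no session is closer to Taper Only than to the assigned arm. An analysis by intervention received will naturally either count that patient with Taper Only or leave the patient out. Both choices replace randomized groups with groups selected after randomization.

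Attendance may well be related to prognosis. The Randomization paragraph aims for the groups to start two to ten weeks after taper initiation, so an early difficult taper can come before the decision to attend and influence it. Patients may also pause or leave the taper at any time. The plan itself expects confounders of compliance, but adjusts for them only in the within-arm attendance regressions.

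At stake is how Hypothesis 2a is read. A sensitivity analysis is meant to show whether the ITT result is robust. If this one came out larger than ITT, it could be taken to mean that the groups work in those who attend, although selection alone can produce that pattern. Neither the attendance regressions nor the unspecified non-completion analysis gives a randomization-based comparison of the arms.

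**Working it through.** **Inputs from Sample Size Calculations and Study Power.** 163 month-12 completers per arm, so 326 behavioral v 163 Taper Only when pooled; 40% v 53.5% success; two-sided 0.05; 80% power.

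**Inputs assumed (not in the documents).** q = share of behavioral-arm patients who attend no session. g = success rate in attenders minus that in non-attenders, for prognostic reasons only.

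**Step 1: reproduce the plan's figure.** For 163 v 326, the pooled rate is (163×0.40 + 326×0.535)/489 = 0.490. The null SE is 0.0480 and the alternative SE 0.0473. Power = Φ((0.135 − 1.96×0.0480)/0.0473) = 80.7%, which matches the stated 80%. A 163 v 163 contrast would give 68.7%, so the stated figure belongs to the pooled contrast used below.

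**Step 2: set up a strict null.** Success is 40% in every randomized arm.

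- Attenders: pA = 0.40 + q·g
- Non-attenders: pN = pA − g
- Comparator if non-attenders are moved: pT = (163×0.40 + 326q·pN)/(163 + 326q)
- Comparator if they are dropped: 0.40

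**Step 3: worked case, q = 20%, g = 20 points.** pA = 0.44 and pN = 0.24. There are 65.2 non-attenders and 260.8 attenders.

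- Moved: pT = (65.2 + 65.2×0.24)/228.2 = 0.354. Difference = 0.440 − 0.354 = 8.6 points. With null SE 0.0444 and actual SE 0.0439, two-sided rejection is 48.8%.
- Dropped: difference = 0.44 − 0.40 = 4.0 points. With SEs 0.0494 and 0.0492, rejection is 12.7%.

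**Step 4: range.**

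| q | g (points) | Moved: difference, rejection | Dropped: difference, rejection |
|---|---|---|---|
| 10% | 10 | +2.5, 8.5% | +1.0, 5.5% |
| 20% | 10 | +4.3, 16% | +2.0, 6.9% |
| 20% | 20 | +8.6, 49% | +4.0, 13% |
| 30% | 20 | +11.3, 72% | +6.0, 22% |
| 40% | 20 | +13.3, 84% | +8.0, 33% |
| 20% | 0 | 0, 5% | 0, 5% |
| 20% | −10 (non-attenders do better) | −4.3, 16% | −2.0, 7% |

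For the reversed row, pA = 0.38, pN = 0.48 and pT = (65.2 + 65.2×0.48)/228.2 = 0.423.

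**Step 5: simulation check.** In 4,000 runs per scenario, the worked case with non-attenders moved rejected in 49.9% (chi-square) and 47.4% (Fisher). ITT on the same data stayed between 4.3% and 5.6% (chi-square) across scenarios.

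**Step 6: the alternative.** The complier estimate is the ITT difference divided by the proportion exposed. Under the null it is 0/0.8 = 0 at q = 20%, whatever g is. Treating the exposed proportion as fixed, its SE is the ITT SE divided by 0.8. At 40% success in both groups the ITT SE is √(0.24×(1/163 + 1/326)) = 4.7 points, so the complier SE is 4.7/0.8 = 5.9 points. The CI is a quarter wider.

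**The case against.** **Consequence.** A reader might infer that the trial's main conclusion is at risk. It is not: the arm comparison is ITT, dropouts are to be included in it, and the disputed analysis is labelled a sensitivity analysis. Nor is it the only check on non-completion.

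**Placement.** A reader might also infer that the plan moves non-attenders to Taper Only because they received exactly that care. The documents do not say so. Receipt is undefined, and the move is an inference from the wording. A non-attender may also hold a workbook and relaxation audio (pain-CBT), a book and exercise CD (CPSMP) or mailed materials, and may have had the virtual-group orientation. This stands. But dropping such patients breaks randomization too, with a smaller bias.

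**Direction and size.** It is tempting to say that the analysis favors the groups. The documents give neither an attendance rate nor any prognosis for non-attenders. Patients tapering well might skip the groups, which reverses the sign, and a 20-point gap is half the base rate. This stands too: the figures show what is possible and are not forecasts. The plan does give covariate-adjusted logistic regression for Hypothesis 2a, but does not extend it to this comparison, and baseline covariates would not capture taper difficulty arising after baseline.

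**The remedy.** The complier estimate assumes that assignment without attendance has no effect. Materials that reach non-attenders and participants' knowledge of their arm both strain that assumption; if it fails, the division can overstate the effect. With exposure set at one session, patients who stop early count as exposed. The estimate also rescales ITT and is not new evidence of benefit. All of this stands and must be stated with the result.

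**Non-study treatment.** Because the tracking statement, "receipt of non-study treatments will be tracked", sits in the CPSMP paragraph and Appendix A has no matching row, a reader might infer unequal measurement across arms. That is an argument from silence. It is not part of this point, and no new survey item is needed.

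**Conclusion.** The point holds as a worthwhile correction to a supporting analysis. An unadjusted comparison by intervention received departs from randomization under either plausible handling of non-attenders. It is biased whenever attendance is related to prognosis. In the illustrative case its false-positive rate is about 49% or 13%, depending on handling, against a nominal 5%. With 40% non-attendance and a 20-point gap, moving non-attenders gives a spurious 13.3 points, about the size of the 13.5-point design difference. These sizes rest on assumed attendance and prognosis, an unadjusted two-proportion test and 326 v 163 completers. The sign follows the sign of the gap, and the bias vanishes when the gap is zero. The ITT inference for Hypothesis 2a stands.

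**What to change.** 1. For behavioral v Taper Only, replace the as-received comparison with a complier average causal effect. Use randomized assignment as the instrument and staff-recorded attendance as the exposure. Taper Only patients are not to receive the study groups, so non-compliance with the groups is one-sided.
2. Define exposure as at least one session in the main version. Add a version with a completion threshold fixed in advance, for patients who stop early. Describe it as more assumption-dependent, because patients below the threshold have had some sessions.
3. Report the estimate with its CI beside the ITT result. State that it has the same null as ITT, has a wider CI, and assumes no effect of assignment without attendance. Say that this assumption is imperfect because materials may reach non-attenders and assignment is unmasked.
4. Keep pain-CBT v CPSMP as ITT.
5. Label the session-attendance regressions, and any as-received result that is retained, as non-randomized and descriptive.
6. Reword the paragraph after Hypothesis 2d so that the success-rate comparison is by assigned arm, in line with ITT.

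The cost is SAP wording and one short analysis of attendance data that the plan already collects. The price in interpretation is the wider CI and the no-effect-without-attendance assumption.
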